**Adjunctive Nitrous Oxide during ED propofol sedation in adults,
a pilot study.**

NCT02410707

Version: 7/1/14

Investigator(s): [name], DO; [name], DO; [name]; [name], CCRC

Objectives

To describe the safety and efficacy of adjunctive nitrous oxide pre-propofol administration for analgesia and pre-procedure anxiolysis during ED procedural sedation and analgesia in adults.

Background

Specific Aims

To measure the rates of hypoxia and respiratory depression requiring a physician intervention in adult patients receiving 50% demand valve nitrous oxide pre-propofol administration during ED procedural sedation and analgesia. Secondary aims include patient, nursing, and physician post procedure satisfaction scores, Ramsay sedation scores, total propofol dose given, length of time spent using nitrous oxide, patient recall of procedure.

Significance

Procedural sedation is the use of sedative, analgesic, and/or dissociative agents to relieve anxiety and pain associated with diagnostic and therapeutic procedures. Propofol has become one of the most commonly used agents for ED procedural sedation.^{1,2} Propofol crosses the blood-brain barrier rapidly. The drug takes effect within approximately 40 seconds, and its

duration of action is approximately six minutes^{2,3} Multiple randomized trials and prospective observational studies have found propofol to be safe and effective for PSA in the emergency department^{3,4,5}. Propofol acts as a sedative and amnestic, but provides no analgesia.

A possible approach is pretreatment with short-acting opioids (eg, fentanyl). Unfortunately, the addition of opioids increases the likelihood of respiratory complications. As an example, fentanyl at a dose of 1.5 mcg/kg increases the risk of respiratory depression. In another study, patients given both alfentanil and propofol required stimulation to induce respiration more often than those given only propofol.⁷ Another alternative to pretreatment with short-acting opioids is to use sub-dissociative doses of ketamine (0.3 mg/kg). Ketamine appears to provide comparable analgesia with less risk of respiratory depression. However, there is no literature that has shown that there is a decreased risk of respiratory depression than with propofol.⁸

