The optimal agent for analgesia before procedural sedation would have effect that is short acting, easy to administer, and with minimal risk to the patient. Nitrous oxide may fit this profile. In pediatric emergency departments, inhaled nitrous oxide was found to be the most common agent for procedural sedation and analgesia.⁸ There is a great deal of literature supporting the use of nitrous oxide in the pediatric population, and the safety and efficacy of its use as a single agent or in concert with a parenteral sedative and/or analgesic is excellent. However, there is a paucity of literature to support or refute the use of nitrous oxide in adults for ED procedural sedation and analgesia.

Nitrous oxide is a colorless gas that diffuses rapidly across the pulmonary alveoli providing analgesia and anxiolysis with minimal sedative effects, rapid induction, and emergence.⁹ Nitrous oxide is a weak sedative agent with the potential for significant analgesic

effects. Noncompetitive antagonist activity at the NMDA receptor along with activation of opioidergic receptors contributes to its anesthetic mechanism.¹⁰ In an RCT (ENIGMA 1) using anesthesia with and without nitrous oxide, there was a small increased risk of myocardial infarction in the nitrous oxide group.¹¹ However, there were patients getting general anesthesia for over two hours; our patients will be receiving 50/50 nitrous oxide for 5-10 minutes maximum, and there are no known cardiac side effects reported during short-term sedation in the literature.¹¹ There are rare adverse events, most often cited as case reports of chronic or acute toxicity causing myeloneuropathies and polyneuropathies.¹²⁻¹⁵

Nitrous oxide has been used in general anesthesia for over 2 centuries, but its use outside of the operating room began when Tunstall introduced the nitrous oxide/oxygen mixture as an analgesic agent during labor.¹⁶ Since this inception, the nitrous oxygen/oxygen mixture has been used readily in the fields of dentistry, gastrointestinal procedures, and children's procedural sedation. Nitrous oxide is often administered via continuous flow or on-demand at a concentration of 50-70%.

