The SEDARA gas mixer system [Linde Gas North America LLC] will be used as our primary nitrous oxide delivery device. It will mix and deliver nitrous oxide and oxygen in a 1:1 ratio, at a fixed concentration of 50%/50%. It uses a patient driven demand valve system that is hand held. This device provides a consistent, fixed 50%/50% blend of nitrous oxide (N₂O) and oxygen (O₂), eliminates the need to titrate, and provides fixed concentrations for controlled and consistent dosing. The device comparator detects dosing imbalance to protect against hypoxic mixtures, it cannot deliver nitrous gas without concurrent oxygen, and the device has an anti-asphyxia valve override. The on demand valve requires patient inspiration to trigger dosing. This portable device scavenges exhaled waste gases for environmental safety, as well as a key mechanism that renders the system inoperable without it for security.

After informed consent, the patient will fill out a pre procedure questionnaire and a 100 mm VAS baseline pain scale. The patient will be given the mask for delivery of nitrous oxide, and instructed on its use. The research associate will mark the time the patient began using the device electronically on the capnostream 20. Once IV access is established, and the team and

patient are ready to begin the procedure, the nitrous oxide mask will be removed, and a 100% NRB mask delivering 15 liters a minute of supplemental oxygen will be placed on the patients face. The loading dose of propofol will then be administered immediately. All sedations in this trial will use propofol 1.0 mg/Kg initial dose, with 0.5 mg/Kg doses titrated to deep sedation. Once the patient is deeply sedated, the procedure will begin.

The subject's clinical data and sedation information (refer to data management) will be entered into a standardized data collection form. The data will be continuously recorded throughout the sedation and recovery periods. Study will end when the subjects recovers back to baseline mental status.

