To assess these outcomes, we will download electronic data from each sedation into a Microsoft Excel database, checked and adjudicated any discrepancies with research associate notations, and generate a graph of the subject's sedation with the X-axis showing time and the Y-axis depicting ETCO₂, SpO₂, respiratory rate, and heart rate. Electronic time stamps noted propofol administration, procedure initiation and completion, adverse events, and physician interventions.

Before study blinding is broken, three investigators will evaluate each graph to code the presence or absence of cerebral hypoxia, peripheral hypoxia and respiratory depression. We will disqualify graphs if they had >35% data loss, unless all three evaluators agreed that there was unequivocal evidence of hypoxia (cerebral and or peripheral) and/or respiratory depression.

6. Withdrawal of Subjects

Participation is voluntary. Subjects may withdraw from this study at any time. If this is the case their data will be deleted. We will record the number of patients that withdraw. Subjects may be withdrawn without their consent if the electronic data cannot be recorded.

Statistical Plan

1. Sample Size Determination

As this is a pilot, prospective, observational trial, no power calculation will be used to measure a difference. In previous propofol studies, approximately 10-30% of patients develop hypoxia, and approximately 50% of patients meet criteria for respiratory depression. Thus, we believe enrolling 100 patients in this observational trial will allow for approximation of any correlations that are measured.

2. Statistical Methods

All clinical observations and demographic data will be summarized using medians with range or means with standard deviations as appropriate. Rate of detection of respiratory depression and hypoxia and timing of these events for each instrument (near-infrared spectroscopy, pulse oximetry, capnography) will be summarized descriptively. Associations among SaO₂, and ETCO₂ will be estimated using spearman's rank correlation coefficient, using within-cluster resampling algorithm. This will allow for estimation of the marginal correlation in the presence of clustered data. Correlations not involving repeated measures data will be estimated with Spearman's rank correlation coefficient. All analysis will be conducted using SPSS software (IBM, Armonk, NY).

Risks to Subjects

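### The 35% data-loss rule covers the whole graph and the codes are only present or absent, so a kept graph can lack SpO2 over the propofol period and is then likely to be coded as free of hypoxia

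*Combined protocol and SAP*

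**What the plan says.** Under Study Design, 5. Data Management, each recording becomes one graph against time, with "the Y-axis depicting ETCO₂, SpO₂, respiratory rate, and heart rate". Then "three investigators will evaluate each graph to code the presence or absence of cerebral hypoxia, peripheral hypoxia and respiratory depression". The rule for missing data is "We will disqualify graphs if they had >35% data loss", with an exception: "unless all three evaluators agreed that there was unequivocal evidence of hypoxia" or of respiratory depression. The section does not say whether loss is counted per signal, over all plotted signals or over time. It does not tie loss to any part of the sedation, and it gives no code for a period that could not be observed.

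Three other statements bear on this. Significance says of propofol that its "duration of action is approximately six minutes", and of the gas that "our patients will be receiving 50/50 nitrous oxide for 5-10 minutes maximum". Study Design, 4. Procedures gives propofol as a loading dose "with 0.5 mg/Kg doses titrated to deep sedation", so the period of action can exceed six minutes. The same section makes loss of the ETCO2 waveform for more than 15 seconds a criterion for respiratory depression; loss of SpO2 has no rule of its own.

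**The concern.** The point concerns graphs that pass the rule, not those it removes. Hypoxia is most to be expected while propofol acts, which may be a small part of a recording that runs on through recovery and may also include the nitrous oxide phase. A limit on overall loss does not protect that part. If SpO2 is missing there and the graph is kept, an evaluator who must choose between present and absent has nothing on the SpO2 trace to support 'present'.

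Measuring the rate of hypoxia is a specific aim, and SpO2 is one of the two primary endpoints. The study has no comparison group, so the observed rate is itself the result. Unobserved risk time counted as event-free would lower that rate, and the published proportion would carry no sign of it.

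**Working it through.** No figure of the plan can be reproduced here: the 35% limit is given without a derivation, and the sample of 100 rests on no power calculation.

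**Inputs from the documents.** Loss limit 35% and four plotted channels (Data Management); propofol action about 6 min and nitrous oxide 5-10 min (Significance); expected hypoxia 10-30% (Sample Size Determination); 100 subjects (Study Design).

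**Assumed, because not stated.** Recording length T; the share f of kept graphs with no SpO2 in the propofol period.

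**Step 1: when is the graph kept?** Lost fraction = (channels lost / channels counted) × (minutes lost / T). The graph is kept if this is 0.35 or less. For a 6-minute gap:

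| How loss is counted | Lost fraction | Graph kept when |
|---|---|---|
| SpO2 as one of four plotted channels | 6/(4T) | any T; SpO2 missing throughout is 1/4 = 25% |
| SpO2 as one of two (with ETCO2), or SpO2 and heart rate both lost out of four | 6/(2T) | T ≥ 3/0.35 = 8.6 min |
| SpO2 channel alone, or time with SpO2 missing | 6/T | T ≥ 6/0.35 = 17.1 min |

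**Step 2: is 17.1 minutes plausible?** Recording needed beyond the phases whose length is given:

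- 10 min nitrous oxide + 6 min propofol: 17.1 − 16 = 1.1 min
- 5 min nitrous oxide + 6 min propofol: 17.1 − 11 = 6.1 min
- nitrous oxide phase not recorded: 17.1 − 6 = 11.1 min

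If repeat doses extend the action to 9 or 12 min (assumed), the third row of the table needs 9/0.35 = 25.7 or 12/0.35 = 34.3 min. The first row is unaffected.

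**Step 3: effect on the rate.** If every affected graph is coded absent and loss is unrelated to events, reported rate = p × (1 − f).

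| f (assumed) | true 10% | true 30% |
|---|---|---|
| 5% | 9.5% | 28.5% |
| 10% | 9% | 27% |
| 20% | 8% | 24% |

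The 95% half-width at n = 100, 1.96 × √(p(1−p)/100), is 5.9 points at 10% and 9.0 points at 30%. At f = 10% the shift of 1-3 points lies inside it.

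**Step 4: the opposite force.** Above 35% loss, only graphs with an unequivocal event stay in. As an illustration, let 10 of 100 graphs exceed the limit and let all their events be unequivocal. A true 30% becomes (27 + 3)/(90 + 3) = 32.3%, and a true 10% becomes (9 + 1)/(90 + 1) = 11.0%.

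**Step 5: the same gap under a windowed rule.** A 6-minute SpO2 gap in a 6-minute window is 100% loss, so the subject is not assessable for hypoxia. With 10 such subjects the expected rate stays at 10% (9/90) or 30% (27/90). The half-width becomes 6.2 or 9.5 points. The all/none bounds are 9/100 to 19/100, or 27/100 to 37/100.

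**The case against.** A reader might infer that the plan orders such graphs to be counted as event-free. It does not. The text asks for presence or absence and is silent on gaps; 'absent' is the likely default, not a written rule.

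A reader might also infer that the gap is hidden from the evaluators. It is not: SpO2 is plotted against time with propofol and procedure stamps, so a six-minute gap would be seen. What is missing is a code in which to record it.

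Other sources may recover events. Electronic data are reconciled with the research associate's notes, adverse events are stamped, and vital signs are flagged when a physician intervenes. If the intervention qualifier in Specific Aims applies to hypoxia as well as to respiratory depression, much of what matters may be captured without the trace. The data collection form is attached but not reproduced, so its contents cannot be judged. This lessens the concern but does not remove it, since a desaturation without intervention need not be flagged. Withdrawal when data cannot be recorded is optional and is not linked to a partial gap.

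The span of the graph is uncertain. Nitrous oxide start is marked on the monitor, but recording is described as covering sedation and recovery, and the graph's listed stamps omit nitrous oxide. If that phase is not plotted, or if doses are repeated, counting on SpO2 or on time would disqualify more of these graphs. This objection stands against any claim about how often the problem occurs. It does not touch the four-channel reading.

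**Conclusion.** The point holds as a possibility that the written rule permits, and it merits a change. On each way of counting in Step 1, some recordings with no SpO2 in the propofol period are kept: at any length if four channels are pooled, and from 17.1 min for a single 6-minute action if SpO2 or time is counted. The effect falls mainly on peripheral hypoxia, because respiratory depression can still be coded from ETCO2.

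The size is not known. At an assumed 10% of kept graphs, all coded absent with no recovery from notes, the loss is 1-3 points. This is smaller than sampling error, but it is systematic and would not average out with more subjects.

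It would be tempting to conclude that the reported hypoxia rate will be too low. The documents do not support that, because the exception above 35% loss raises the rate and neither share is known. Two opposing biases of unknown size are still a reason to define the rule, and one definition deals with both.

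**What to change.** Amend Data Management as follows.

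- Assess loss separately for SpO2 and ETCO2, within a window from the propofol loading dose to the later of procedure completion or 6 minutes after the last propofol dose.
- Add a third code, 'not assessable', for a signal above the loss limit in that window, applied whatever the outcome. It replaces the exception for unequivocal events.
- Report hypoxia among assessable subjects with that denominator stated, and give bounds that count all and none of the non-assessable subjects as events. List separately any hypoxia noted at the bedside in non-assessable subjects, so that no observed event is lost.

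The cost is one paragraph and a short program on stored data. Dose times and procedure completion are already recorded, so no further subjects or measurements are needed. The downside is a slightly smaller denominator and a wider interval: with 10 non-assessable subjects, the half-width rises from 5.9 to 6.2 points at a 10% rate and from 9.0 to 9.5 points at 30%.

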Vital signs will be flagged electronically when a physician intervenes for clinical respiratory depression. Respiratory depression will be defined as peripheral SaO₂ below 92%, ETCO₂ level above 50, a rise or decrease of 10% above or below baseline, the loss of the ETCO₂ waveform for more than 15 seconds. Level of consciousness will be determined using the modified Ramsay scale, which will be recorded at baseline and at the point of deepest sedation. Once the procedure is complete, and the patient is deemed back to their mental status baseline, they will fill out a post procedure satisfaction questionnaire, and a 100mm VAS scale. They will be asked about procedure recall. The physician will also fill out a post procedure questionnaire.

5. Data Management

A standardized data collection form will be used to collect clinical data and a USB drive to collect electronic vital sign data. Initial data gathered will include age, gender, weight, and baseline vital signs (BP, HR, RR, peripheral SpO₂, and ETCO₂). Other information collected will be the elapsed time of nitrous oxide use, start time (when protocol was given), time (when patient returns to baseline), elapsed time in seconds under sedation (from start time to end time),

medications administered, repeated doses and times for every administered medication, total dose of each medication administered, adverse events, and interventions aimed at correcting respiratory depression. Level of consciousness using the modified Ramsay scale will also be recorded at baseline and at set intervals during sedation.

The electronic monitoring data will be continuously recorded into the USB drive throughout the sedation and recovery periods. The Capnostream 20 ETCO₂ monitor (Oridian Medical, Needham, MA) is capable of sampling and recording ETCO₂ and pulse SaO₂ every 5 seconds. A patient identifier will be recorded to link the subject and the electronic monitoring data without compromising his/her confidentiality. At the completion of the sedation, all device data will be transmitted to a password-protected Excel/SPSS spreadsheet for analysis. The research associate is responsible for recollection and storage of the data. Only the primary investigators, the study coordinator, and the research associates will have access to such.

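### Deleting the data of subjects who withdraw, and keeping only a count, can remove recorded events from a single-group safety description

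*Combined protocol and SAP*

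**What the plan says.** Section 6, Withdrawal of Subjects, makes participation voluntary and sets no end to the right to withdraw. For a subject who does so it states: "If this is the case their data will be deleted". The next sentence sets out what is kept: "We will record the number of patients that withdraw". There is no exception for adverse events, for data collected before the withdrawal, or for subjects already exposed. A separate sentence covers withdrawal by the study when monitoring fails ("Subjects may be withdrawn without their consent if the electronic data cannot be recorded"). It does not say what happens to those data, and this point does not depend on it.

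Exposure and events are recorded well before a subject finishes. Under section 4, Procedures Involved in the Research, the mask is given after consent, and "The research associate will mark the time the patient began using the device electronically on the capnostream 20". Under section 5, Data Management, the data form includes "adverse events, and interventions aimed at correcting respiratory depression".

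The Statistical Plan defines no safety population, no handling of withdrawn subjects and no sensitivity analysis. The Objectives section gives description of safety and efficacy as the purpose. Study Design describes a non-randomized convenience sample of 100.

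**The concern.** With no comparator, the observed event rates are the safety finding. If leaving the study is related to having had an event, for example agitation or nausea on the gas, deletion biases those rates. Once the records are gone, nobody can check whether it did. A bare count does not show whether a withdrawal came before or after exposure, or why it happened.

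The time available for such withdrawals is short. The Significance section says "our patients will be receiving 50/50 nitrous oxide for 5-10 minutes maximum". Propofol follows immediately, and "Study will end when the subjects recovers back to baseline mental status". A deeply sedated subject cannot ask to leave, so the outcomes are exposed to different degrees:

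- **Nitrous oxide phase.** Events here are the most exposed, because the subject is awake and can withdraw straight afterwards.
- **Hypoxia and respiratory depression under propofol.** These are lost essentially only if the subject withdraws after recovery.
- **Patient satisfaction.** At the end, "they will fill out a post procedure satisfaction questionnaire". A score is deleted only if the subject completes the form and then withdraws. For earlier withdrawals it is ordinary missing data.
- **A rare serious event.** One deletion changes the finding from one such event to none.

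**Working it through.** The sample of 100 is not derived from a formula, so there is no planned figure to reproduce. The question is how far deletion could move a reported rate.

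**Inputs from the document**
- N = 100 (Study Design).
- Planning rates: hypoxia 10% to 30%, respiratory depression about 50% (Sample Size Determination).
- About 10% mild side effects with nitrous oxide as a single agent (Significance). This comes from a different setting and is used here only as an illustrative rate for the nitrous oxide phase.

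**Assumed inputs**
- w, the share of exposed subjects who withdraw after exposure: 3%, 5% or 10%.
- p, the event rate among those who withdraw: 0% to 100%.

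**Formula.** The reported rate b is the rate in subjects who stay. The true rate in all exposed subjects is w × p + (1 − w) × b.

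**Nitrous oxide phase, b = 10%: true rate (%)**

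| w | p = 0% | 10% | 30% | 50% | 100% |
|---|---|---|---|---|---|
| 3% | 9.7 | 10.0 | 10.6 | 11.2 | 12.7 |
| 5% | 9.5 | 10.0 | 11.0 | 12.0 | 14.5 |
| 10% | 9.0 | 10.0 | 12.0 | 14.0 | 19.0 |

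There is no bias when p = b. As a yardstick, the exact (Clopper-Pearson) 95% interval for 10/100 is 4.9% to 17.6%, and 14 of the 15 cells fall inside it. To reach the upper limit of 17.62%:
- if all withdrawers had events, w = (17.62 − 10)/(100 − 10) = 8.5%;
- if half did, w = (17.62 − 10)/(50 − 10) = 19.1%.

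The interval describes sampling error only. A true rate inside it does not mean the bias is accounted for.

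In the other direction, suppose 10 of 100 exposed subjects had the event and 5 of those 10 withdrew. The report would show 5/95 = 5.3% (exact 95% interval 1.7% to 11.9%).

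**Respiratory outcomes, w = 3% after recovery, p from 0% to 100%**
- b = 10%: 0.97 × 10 = 9.7% to 9.7 + 3 = 12.7%
- b = 30%: 29.1% to 32.1%
- b = 50%: 48.5% to 51.5%

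**Rare serious event.** One event in 100 is 1.0% (exact 95% interval 0.03% to 5.4%). If that subject withdraws, the report shows 0/99, which is 0% with an upper limit of 3.7%.

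**What recording exposure would add.** Suppose 100 are enrolled, 10 withdraw and 9 of the remaining 90 have an event.
- Only the count is known: the rate lies between 9/100 = 9.0% and 19/100 = 19.0%.
- Only 3 of the 10 are known to have inhaled the gas: it lies between 9/93 = 9.7% and 12/93 = 12.9%.

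**The case against.** The strongest reply is that the effect will probably be small:

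- The primary aim concerns hypoxia and respiratory depression, which are lost only if someone leaves once participation is practically over. At w = 3% the shifts are far smaller than the sampling intervals at N = 100 (4.9% to 17.6%, 21.2% to 40.0% and 39.8% to 60.2% for 10%, 30% and 50%).
- Side effects of the gas are not among the listed endpoints.
- Stopping the gas is not withdrawing from the study. The device is hand-held and triggered by the patient's own breathing, so a subject who dislikes it can stop inhaling and still go on to propofol. That removes the most obvious route from an event to a deletion.
- If withdrawal is unrelated to events and w = 3%, a single serious event has only a 3% chance of being deleted.
- The count that is kept already allows best-case and worst-case bounds.
- Deletion may reflect a promise in the consent form, which is not in our copy.

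Much of this stands. It lowers the likely frequency of the problem and shows that the common respiratory outcomes are little affected. It does not change what the rule does. Adverse events are collected on the data form and safety is the stated objective, so they matter even though they are not listed endpoints. The count gives bounds that are wider than they need be, and it cannot restore a deleted serious event. A consent promise would limit what can be kept, and the remedy allows for that.

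**Conclusion.** The concern holds. Applied as written, the rule removes exposed subjects and their recorded events from a single-group safety description, and nothing elsewhere in the document restores them.

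The size cannot be determined, because no withdrawal rate is given and all values of w and p are assumptions. On those assumptions the effect on the respiratory outcomes is small. For the nitrous oxide phase it is moderate at most, with a true rate of 9.0% to 19.0% behind a reported 10%. For a single serious event it can be decisive, because one event becomes none. Bias arises only if withdrawal after exposure is related to events, and deletion makes that impossible to check.

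The data collection form and consent form are not in our copy. They may add detail or explain the deletion. The finding concerns the protocol text, and the point should be fixed.

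**What to change.** Replace the deletion sentence in section 6 with: *No further data are collected after withdrawal; data collected up to that time are kept, as far as consent and the ethics committee allow.*

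Then add to sections 5 and 6 and the Statistical Plan:

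- The safety denominator is all subjects who inhaled nitrous oxide. For sedation-related respiratory rates it is those who also received propofol.
- For each withdrawal, record the time, the exposure status (none, nitrous oxide only, nitrous oxide and propofol) and the reason if one is offered.
- If a subject asks for erasure, count that subject as missing and report best-case and worst-case bounds for the event rates.

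The cost is a protocol change with matching consent wording, ethics committee approval and slightly more reporting. No study procedure is added. How much the consent form and data collection form would need to change cannot be judged from our copy.

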2. Inclusion and Exclusion Criteria

- i. Inclusion criteria: All spontaneously breathing subjects, 18 years of age and older, with an American Society of Anesthesiologists (ASA) Physical Status Classification 1 or 2, who will be receiving sedation for an ED procedure.

Written informed consent will be obtained from all subjects.

- ii. Exclusion criteria: Subjects with underlying conditions that could affect ventilation, perfusion, or metabolism including intubated subjects, subjects with clinical signs of cardiopulmonary instability, major trauma, shock, sepsis, ASA class 3, 4, and 5. Also those unable to provide informed consent, nursing home residents, age less than 18 years, non English speaking, pregnant women, subjects under police custody, or physician discretion.

3. Study Endpoints

- i. Primary:

1. ETCO₂ measured q 20 milliseconds seconds
2. SpO₂ measured q 20 milliseconds seconds

- ii. Secondary Endpoints

1. A baseline reading of the vital signs (heart rate, respiratory rate, peripheral SaO₂ and ETCO₂)
2. Physician interventions (verbal or physical stimulation, airway repositioning, additional oxygen, positive pressure ventilation, endotracheal intubation)
3. Level of sedation (Ramsay Score)
4. Patient Demographics
5. Patient recall of procedure
6. Total propofol dose
7. Total elapsed time of nitrous oxide use
8. Patient and physician procedure satisfaction score

4. Procedures Involved in the Research

Initial medical assessment will be made in accordance with established clinical procedures, including the history, physical examination, and vital signs. If by clinical assessment the patient meets eligibility criteria, then they will be approached by a research associate for enrollment in the study. After informed consent is obtained and prior to starting the sedation, standard vital sign monitoring will be placed on the patient (electrocardiogram, non-invasive blood pressure monitoring, pulse oximetry, and capnography). Level of consciousness will be determined using the modified Ramsay scale, which will be assessed at baseline. The Capnostream 20 ETCO₂ monitor will be used as the primary device to measure ETCO₂, with a nasal cannula capable of delivering supplemental oxygen and measuring ETCO₂ (Oridion Medical, Needham, MA).

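### A recording failure may remove an exposed subject from the whole study, although the form-based and questionnaire-based safety outcomes can still be used

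*Combined protocol and SAP*

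**What the plan says.** Section 6 of the Study Design, Withdrawal of Subjects, contains two rules. The first covers subjects who choose to leave: "If this is the case their data will be deleted", and "We will record the number of patients that withdraw". The second is a decision of the study team: "Subjects may be withdrawn without their consent if the electronic data cannot be recorded". The second rule sets no time limit relative to exposure and no criterion beyond the failure itself. It does not say whether data already collected are kept, analysed or deleted.

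Section 5, Data Management, describes two sources: "A standardized data collection form will be used to collect clinical data and a USB drive to collect electronic vital sign data". The information to be collected includes "total dose of each medication administered, adverse events, and interventions aimed at correcting respiratory depression". Section 4, Procedures Involved in the Research, places clinical and sedation information on the form. It obtains satisfaction after recovery ("they will fill out a post procedure satisfaction questionnaire, and a 100mm VAS scale"), asks the patient about recall, and has the physician complete a questionnaire as well. The secondary endpoints in section 3 include "Physician interventions (verbal or physical stimulation, airway repositioning, additional oxygen, positive pressure ventilation, endotracheal intubation"), Ramsay score, recall, total propofol dose and satisfaction.

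Some items are also electronic. Section 5 says: "Electronic time stamps noted propofol administration, procedure initiation and completion, adverse events, and physician interventions". Section 4 has the start of nitrous oxide marked on the monitor and vital signs flagged electronically when a physician intervenes.

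**The concern.** The rule acts on the subject when only the signal is missing. A subject may have inhaled nitrous oxide, received propofol, needed an airway intervention that was written on the form, and answered the questionnaires. That subject can still leave the study because the monitor or USB drive failed.

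The stated objective is to describe safety and efficacy, and no analysis set of all exposed subjects is defined. At stake are the rates of interventions and adverse events and the summaries of dose, sedation depth, recall and satisfaction. Each could rest on fewer subjects than were exposed. Because the rule is permissive and has no time limit, nothing prevents the decision from being made after the outcome is known. The only accounting is a count of patients who withdraw. The plan asks for no reason, timing, exposure status or outcome, so a reader of the results could not judge whether the exclusions mattered.

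**Working it through.** No figure in the plan depends on this rule. The sample of 100 is stated without a power or precision calculation and without an allowance for recording failure, so there is nothing to reproduce.

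**Step 1. Which outcomes need the recording?**

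- Need it: ETCO₂, SpO₂, and hypoxia and respiratory depression as coded from the graphs.
- Have another source: occurrence of interventions and adverse events, propofol dose, Ramsay score, recall, satisfaction.
- Mixed: nitrous oxide start time and the timing of interventions and adverse events. These are marked electronically and survive only if also on the form.

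Withdrawing the whole subject is therefore broader than the missing data require. The plan already has a narrower tool: in section 5, a graph with more than 35% data loss is disqualified as a graph, and the subject is not removed.

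**Step 2. Possible bias in a form-based rate.** Let p be the true rate among all exposed subjects, w the share withdrawn for recording failure, and RR the event risk in withdrawn relative to retained subjects. If r is the rate in retained subjects, then p = (1 − w)·r + w·RR·r, so

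r = p / [(1 − w) + RR·w].

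The documents give no value for w, RR or the intervention rate, so all inputs are assumptions. With p = 10%:

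| w | RR = 1 | RR = 2 | RR = 3 |
|---|---|---|---|
| 5% | 10.0% | 9.5% | 9.1% |
| 10% | 10.0% | 9.1% | 8.3% |
| 20% | 10.0% | 8.3% | 7.1% |

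For example, 0.10 / (0.95 + 3 × 0.05) = 0.10 / 1.10 = 9.1%. If the true rate were 30%, then w = 5% would give 30.0%, 28.6% and 27.3% for RR = 1, 2 and 3.

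**Step 3. Arithmetic limits.** With 100 exposed, 10 events and 5 withdrawn, the retained rate lies between (10 − 5)/95 = 5.3% and 10/95 = 10.5%. The rate can move in either direction, depending on who is withdrawn.

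**Step 4. Precision when failure is unrelated to events.** The approximate 95% half-width 1.96·√[p(1 − p)/n] at p = 10% is 5.9 points with n = 100, 6.0 with 95, 6.2 with 90 and 6.6 with 80. For an assumed 1% adverse event, the chance of seeing at least one case, 1 − 0.99ⁿ, is 63.4% with 100 subjects, 61.5% with 95 and 59.5% with 90.

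**The case against.** The strongest reply is that this is a small, single-group, descriptive pilot with a permissive rule. The primary endpoints are ETCO₂ and SpO₂, and a subject without a recording cannot contribute to them under any rule. That stands: the fix recovers nothing for the signal-based primary endpoints. What is at stake is the secondary and safety summaries.

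A reader might go further and infer that safety data are lost, and lost selectively, so that intervention rates are biased downward. The documents do not support this, for three reasons.

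- Deletion is stated only for subjects who withdraw themselves. The fate of data after a withdrawal by the study team is simply not given.
- Nothing links recording failure to outcome. One might suppose that ventilating or intubating a patient displaces the mask and sampling cannula. That would interrupt ETCO₂, but it need not stop pulse oximetry or the recording as a whole. Partial loss falls more naturally under the graph rule. Loss of the ETCO₂ waveform for over 15 seconds is itself a criterion for respiratory depression, so it would tend to add a coded event.
- A large bias needs an extreme assumption. If 5 of 100 recordings fail and 3 of those 5 subjects had an intervention, against 7 of the other 95, the rate reads 7/95 = 7.4% instead of 10.0%, a relative understatement of 26%. But this implies a risk ratio of (3/5)/(7/95), about 8. Even 7.4% lies inside the exact 95% interval for 10/100, which is 4.9% to 17.6%.

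Nor are the sources cleanly separate, since several timings exist electronically. None of this answers the narrower point: the rule as written allows exposed subjects with usable data to be excluded, and says nothing about those data.

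**Conclusion.** The concern holds in a limited form. Section 6 allows a whole exposed subject to be withdrawn, at discretion and at any time, because of a recording failure, and leaves the subject's other data undefined. Outcomes with a form or questionnaire source can be excluded without need.

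The certain cost of each such exclusion is precision, and it is small: at an assumed 10% rate, the half-width grows from 5.9 to 6.0 points if 5 of 100 are withdrawn. Bias is conditional. It is nil if failure and the decision to withdraw are unrelated to events. With an assumed 5% failure and a risk ratio of 1 to 3, a true 10% would read 10.0% to 9.1%. The failure rate, the risk ratio and the 10% are all assumptions. The point does not rest on their size, because a narrower rule costs almost nothing and removes the question for the form-based outcomes.

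**What to change.** Amend section 6 as follows:

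- Limit withdrawal for recording failure to failures found before the first nitrous oxide inhalation.
- After exposure, keep the subject in the denominator for all outcomes from the form or questionnaires: interventions, adverse events, propofol dose, Ramsay score, recall and satisfaction.
- Treat as missing only the endpoints that need the electronic record: ETCO₂, SpO₂, graph-coded hypoxia and respiratory depression, and electronic timings not also on the form.
- Report how many exposed subjects lack a recording, when and why it failed, and how many of them had an intervention or adverse event.

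The cost is a short amendment and one line in the report. The drawback is that signal-based and form-based endpoints will have different denominators, so each table should state its own.
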